2.1.2 Secondary Objectives

- To demonstrate the efficacy of SARS-CoV-2 rS with Matrix-M1 adjuvant in the prevention of virologically confirmed (by PCR to SARS-CoV-2), symptomatic COVID-19, when given as a 2-dose vaccination regimen, as compared to placebo, in adult participants regardless of their serostatus at baseline.
- To assess the efficacy of SARS-CoV-2 rS with Matrix-M1 adjuvant on SARS-CoV-2 seropositive adult participants requiring specific medical interventions as compared to placebo.
- To assess the efficacy of SARS-CoV-2 rS with Matrix-M1 adjuvant on mild COVID-19 symptoms as compared to placebo.
- To assess the efficacy of SARS-CoV-2 rS with Matrix-M1 adjuvant on occurrence of asymptomatic or undetected infections with SARS-CoV-2 as compared to placebo.
- In a subset of adult participants, to evaluate the immunogenicity of SARS-CoV-2 rS with Matrix-M1 adjuvant as compared to placebo.
- To evaluate safety in terms of SAEs and medically attended adverse events (MAAEs) related to study vaccination in all adult participants during the entire study period.
- To evaluate safety in terms of AESI, which encompasses potential immune-mediated medical conditions (PIMMCs) and AESIs relevant to COVID-19, including possible vaccine-enhanced disease, in all adult participants at any time after the first dose.
- In a subset of adult participants, to evaluate the safety and reactogenicity in terms of solicited local and systemic adverse events (AEs) for 7 days after each study vaccination.
- To evaluate safety in terms of all MAAEs for 14 days after second vaccination and unsolicited AEs for 21 days after first study vaccination and 28 days after second study vaccination.

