2.2.2.2 Other Secondary Endpoints

- First occurrence of virologically confirmed (by PCR to SARS-CoV-2), symptomatic mild, moderate, or severe COVID-19, with onset at least 7 days after second study vaccination (e.g., Day 28) in adult participants regardless of their serostatus at baseline.
- First occurrence of COVID-19 requiring hospitalisation, intensive care unit (ICU) admission or mechanical ventilation linked to any virologically confirmed (by PCR to SARS-CoV-2) COVID-19 with onset at least 7 days after second study vaccination (e.g., Day 28) in adult participants regardless of their serostatus at baseline.
- First occurrence of virologically confirmed (by PCR to SARS-CoV-2), symptomatic mild COVID-19 (with no progression to moderate or severe COVID-19 during the course of the COVID-19 episode) with onset at least 7 days after second study vaccination (e.g., Day 28) in adult participants regardless of their serostatus at baseline.
- First occurrence of laboratory-confirmed (by PCR or nucleocapsid [N] protein serology to SARS-CoV-2) symptomatic or asymptomatic COVID-19 with onset at least 7 days after second study vaccination (e.g., Day 28) in adult participants regardless of their serostatus at baseline.
- Analysis of antibodies binding to the SARS-CoV-2 spike (S) protein by enzymelinked immunosorbent assay (ELISA) at Day 0 (baseline) and Day 35 (14 days after second study vaccination).
- The occurrence and relationship to study vaccination of SAEs and MAAEs related to study vaccination (in all adult participants) during the entire study period.
- The occurrence and relationship to study vaccination of AESIs and PIMMCs (in all adult participants) during the entire study period.
- The occurrence and severity of reactogenicity in terms of solicited local and systemic AEs (in all sub-study participants) for 7 days after each study vaccination.

• The occurrence, severity, and relationship to study vaccination of all MAAEs for 14 days after second vaccination and unsolicited AEs (in all adult participants) for 21 days after first study vaccination and 28 days after second study vaccination.

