^o The HAI assay will be performed in the approximately 400 participants in the licensed seasonal influenza co-administration sub-study.

^p Cell-mediated immune responses, as assessed by ELISpot ± intracellular cytokine staining, will be performed in approximately 450 participants in the Cell-mediated Assay Subset.

^q Study vaccination on Day 0 will consist of study vaccine plus, in the seasonal influenza vaccine co-administration sub-study, a single dose of licensed influenza vaccine. Study vaccination on Day 21 will consist of study vaccine.

^r Solicited AEs (e.g., local and general systemic reactogenicity symptoms) will be captured in the Safety Subset of approximately 2,000 participants and in the first approximately 400 participants who qualify for the seasonal influenza vaccine co-administration sub-study. On study vaccination days, participants will remain in clinic for at least 30 minutes to be monitored for any severe reactogenicity. Severe reactions will be noted as AEs on day of study vaccination.

⁵ Participants will monitor for COVID-19 symptoms. This will include provision of a Study ID Card that provides details on study participation, study site contact information and assessment of symptoms of suspected COVID-19 (see Table 2-2). Instructions to participants to contact the study site within 24 hours for symptoms of suspected COVID-19 will be given. A participant with suspected or confirmed COVID-19 will be asked to complete a COVID-19 symptom diary for 10 days. The Study ID Card should be presented to healthcare providers not affiliated with the study who encounter participants with symptoms of suspected COVID-19.

^t A participant with suspected or confirmed COVID-19 will be asked to complete the COVID-19 symptom diary. Participants should start the diary on their first day of symptoms and complete this diary daily for a minimum of 10 days even if their symptoms have resolved and regardless of any SARS-CoV-2 PCR results. They should continue the diary beyond 10 days if they have any ongoing symptoms related to the episode and should continue to do so until all symptoms have resolved.

- ^u All unsolicited AEs are to be reported from the time of first study vaccination until 21 days after first study vaccination and 28 days after second study vaccination in all participants.

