4.3 Other Considerations

Participants meeting any of the following criteria may have planned study vaccination deferred for a later date, but these criteria are not exclusionary for study enrolment.

- Respiratory symptoms in the past 3 days (i.e., cough, sore throat, difficulty breathing). Participant may be vaccinated once all symptoms have been resolved for > 3 days. Out-of-window study vaccination is allowed for this reason (see NOTE).
- Temperature of > 38°C within 24 hours of planned study vaccination (site measured or participant measured). Participant may be vaccinated once the fever has resolved and there has not been any temperature measured as being > 38°C for > 3 days. Out-of-window study vaccination is allowed for this reason (see NOTE).

NOTE: PCR testing for SARS-CoV-2 is likely to be indicated for either of the above reasons or if COVID-19 is suspected based on other symptoms, potential exposure to SARS-CoV-2 infection through either close contacts or based on local epidemiology. If a participant has a positive PCR for SARS-CoV-2 prior to enrolment that participant will not be eligible and will be considered a screen failure.

- Participants having any symptoms or signs of possible COVID-19 infection (Table 2-2) that may also be due to post-vaccination reactogenicity within 7 days of either study vaccine dose will NOT be required to be tested for SARS-CoV-2 PCR.
- Any participant with a new positive PCR-confirmed SARS-CoV-2 infection occurring from Screening and prior to second study vaccination will not be removed from the study but must meet health requirements before receiving the second study vaccination.
- Any participant who has a positive PCR for SARS-CoV-2 between the first and second study vaccination should also have PCR testing for SARS-CoV-2 on the day of the subsequent study vaccination, but the results of the PCR test are not needed before study vaccination can be given.
- Any participant with a new positive PCR-confirmed SARS-CoV-2 infection occurring from Screening and prior to the end of immunogenicity assessments will be removed from applicable immunogenicity analyses as defined in the SAP.

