6.1.5.2 Follow-up COVID-19 Surveillance Visit

A Follow-Up COVID-19 Surveillance Visit will occur approximately 7 (+ 3) days after the Initial COVID-19 Surveillance Visit to ascertain worsening/progression of COVID-19 symptoms.

- Review of medical history, including prior and concomitant medical conditions, recent vaccinations (≤ 90 days), and significant surgical procedures.
- Prior and concomitant medications. Concomitant medications include all medications (including vaccines) taken by the participant.
- Vital sign measurements, including respiratory rate, blood pressure, pulse rate, pulse oximetry, and oral temperature (or via forehead/ear reader).
- Symptom-directed (targeted) physical examination, including a respiratory assessment.
- COVID-19 Symptom Diary. A participant with suspected or confirmed COVID-19 will be asked to complete the COVID-19 symptom diary. Participants should start the diary on their first day of symptoms and complete this diary daily for a minimum of

10 days even if their symptoms have resolved and regardless of any SARS-CoV-2 PCR results. They should continue the diary beyond 10 days if they have any ongoing symptoms related to the episode and should continue to do so until all symptoms have resolved.

• Assessment of MAAEs (related to study vaccination), SAEs, and AESIs.

6.1.6 3 Months (± 15 days) After Second Study Vaccination

All participants will have the following procedures performed:

- Prior and concomitant medications. Concomitant medications include all medications (including vaccines) taken by the participant.
- Blood sampling for SARS-CoV-2 (ELISA for anti-N-protein serology) in all participants.
- Monitoring for COVID-19. Participants will monitor for COVID-19 symptoms. This will include provision of a Study ID Card that provides details on study participation, study site contact information, and assessment of symptoms of suspected COVID-19 (see Table 2-2). Instructions to participants to contact the study site within 24 hours for symptoms of suspected COVID-19 will be given. A participant with suspected or confirmed COVID-19 will be asked to complete a COVID-19 symptom diary for 10 days. The Study ID Card should be presented to healthcare providers not affiliated with the study who encounter participants with symptoms of suspected COVID-19.
- Assessment of MAAEs (related to study vaccination), SAEs, and AESIs.

6.1.7 6 Months (± 15 days) After Second Study Vaccination

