6.4 Safety Assessments

The timing and frequency of all safety assessments are listed in the SOE (Table 3-1).

After each study vaccination, including the licensed seasonal influenza vaccine for participants in the seasonal influenza vaccine co-administration sub-study, participants will remain under observation at the study site for at least 30 minutes for the presence of any acute reactions and solicited AEs. Solicited AEs, collected through an electronic diary (e-Diary), will be recorded at each study vaccination visit from the time of study vaccination until 7 days after study vaccination in all participants in the seasonal influenza vaccine co-administration sub-study and a subgroup of all other participants. Participants in the licensed seasonal influenza vaccine co-administration sub-study will record local reactogenicity for the study vaccine injection site only.

All participants will be assessed for unsolicited AEs from the time of first study vacation until Day 49; SAEs will be assessed from the time the informed consent is signed until completion of the participant's last study-related procedure; all MAAEs will be reported from the time of first study vaccination until Day 35; MAAEs related to study vaccination and AESIs will be reported from the time of first study vaccination until completion of the participant's last study-related procedure. All AEs will be followed until resolution or until clinically stable.

Safety assessments will include monitoring and recording of solicited (local and systemic reactogenicity events) and unsolicited AEs; MAAEs; AESI; SAEs; vital sign measurements on day of study vaccinations; and physical examination findings. COVID-19 severity will be categorised as virologically confirmed, mild, moderate, or severe according to protocol-specified criteria (Table 2-1). Recording of solicited and unsolicited AEs may be conducted by electronic data capture (EDC)/reporting. PIMMCs and AESIs specific to potential disease

enhancement for COVID-19 will also be monitored (see Section 9.5 [Appendix 4] for details).

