7.3.3 Safety Analyses

Solicited AEs (e.g., local and general systemic reactogenicity symptoms) will be captured in the Safety Subset of approximately 2,000 participants and in the seasonal influenza vaccine co-administration sub-study of approximately 400 participants.

Numbers and percentages (with 95% CIs based on the Clopper-Pearson method) of participants with solicited local and systemic AEs through 7 days after each study vaccination will be summarised by study vaccine group and the maximum toxicity grade over 7 days after each study vaccination. The duration of solicited local and systemic AEs after each study vaccination will also be summarised by treatment group.

Unsolicited AEs will be coded by preferred term and system organ class using the latest version of the MedDRA and summarised by study vaccine group as well as by severity and relationship to study vaccine. AEs through 49 days after first study vaccination; all MAAEs

through 35 days after first study vaccination; and MAAEs related to study vaccine; SAEs; or AESI through EOS will be listed separately and summarised by study vaccine group.

Vital sign measurements will be summarised by study vaccine group using descriptive statistics at baseline and following study vaccination.

Concomitant medications will be provided in a data listing with preferred drug name as coded using the World Health Organisation drug dictionary.

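### Unsolicited AEs and all MAAEs are promised to 28 and 14 days after dose 2, but the analysis cuts them at 49 and 35 days after dose 1; the two agree only if dose 2 is on Day 21

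*Protocol*

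**What the plan says.** Two sets of windows appear in the protocol.

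**Counted from dose 2.** The endpoint in section 2.2.2.2 covers "unsolicited AEs (in all adult participants) for 21 days after first study vaccination and 28 days after second study vaccination". For MAAEs of any cause, the same endpoint runs to 14 days past dose 2. The secondary objectives (section 2.1.2) and the synopsis say the same. Footnote u of Table 3-1 has unsolicited AEs reported "until 21 days after first study vaccination and 28 days after second study vaccination in all participants".

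**Fixed days.** Section 6.4 assesses unsolicited AEs until Day 49 and states that "all MAAEs will be reported from the time of first study vaccination until Day 35". Footnote v, section 6.4.1.1.4 and the synopsis repeat Day 35 for all MAAEs. Section 7.3.3 and the safety-analysis text of the synopsis name the anchor outright: "AEs through 49 days after first study vaccination", and all MAAEs through 35 days, again after the first vaccination.

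**Timing of dose 2 and of the visits.** Dose 2 is due on Day 21 with a +7-day window (section 3). Section 4.3 allows it outside the window after respiratory symptoms, fever or another acute illness, and gives no upper limit. Footnote b of Table 3-1 schedules the visits after dose 2 from the actual vaccination date. The visit labelled Day 35 is at least 14 days after dose 2, +7 days. It is the last one at which Table 3-1 and section 6.1 list unsolicited AEs. The 3-month visit (section 6.1.6) lists only "Assessment of MAAEs (related to study vaccination), SAEs, and AESIs".

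**The concern.** The same secondary safety endpoint has two definitions, and the one in the analysis section is the narrower whenever dose 2 comes after Day 21. A programmer who follows section 7.3.3 would discard events that the endpoint includes. The visit labelled Day 35 moves with dose 2 and asks for all MAAEs (section 6.1.4), so some MAAEs collected there as planned would fall after the stated analysis cut-off.

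What is at stake is the absolute incidence of unsolicited AEs and all MAAEs after dose 2, in all of the roughly 15,000 participants. Sites, data managers and programmers could also each apply a different window. A second, weaker worry is that no visit lists unsolicited AEs for the last part of the 28 days.

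**Working it through.** **Inputs.** Promised windows after dose 2: 28 days (unsolicited AEs) and 14 days (all MAAEs), from section 2.2.2.2. Cut-offs after dose 1: 49 and 35 days, from section 7.3.3. Dose 2 on day *d*: 21 to 28 in window (section 3), later if deferred for illness (section 4.3).

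**Reproducing the plan's figures.** 21 + 28 = 49 and 21 + 14 = 35. Both cut-offs are exact for dose 2 on Day 21.

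**Days dropped for dose 2 on day *d*.**
- Unsolicited AEs: 28 − (49 − *d*) = *d* − 21.
- All MAAEs: 14 − (35 − *d*) = *d* − 21, up to the full 14.

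| Dose 2 on | AE days kept / dropped (of 28) | MAAE days kept / dropped (of 14) |
|---|---|---|
| Day 21 | 28 / 0 | 14 / 0 |
| Day 25 | 24 / 4 (14%) | 10 / 4 (29%) |
| Day 28 (end of window) | 21 / 7 (25%) | 7 / 7 (50%) |
| Day 35 (out of window) | 14 / 14 (50%) | 0 / 14 (100%) |

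The documents do not say how dose 2 dates will be distributed. If they were uniform over Days 21 to 28 (an assumption), the mean loss would be (0 + 1 + … + 7)/8 = 3.5 days: 3.5/28 = 12.5% of the AE window and 3.5/14 = 25% of the MAAE window.

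**Effect at the visit labelled Day 35.** With dose 2 on Day 28 this visit falls between Day 28 + 14 = 42 and Day 28 + 21 = 49. An MAAE with onset on Days 36 to 42 lies 8 to 14 days after dose 2. It belongs to the endpoint and is asked for at the visit, but it lies beyond the 35-day analysis cut-off.

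**Visit coverage, a separate matter.** The last visit listing unsolicited AEs is 14 to 21 days after dose 2. That leaves 28 − 14 = 14 days (50%) down to 28 − 21 = 7 days (25%) without a later visit that lists them, even when dose 2 is exactly on Day 21.

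**Recall if those days are asked about at 3 months.** Taking 3 months as 90 days (an assumption), the visit is 75 to 105 days after dose 2. The shortest recall is 75 − 28 = 47 days, about 7 weeks. The longest is 105 − 14 = 91 days, which is 13 weeks.

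**A smaller wording gap.** Read literally, footnote u stops at 21 days after dose 1 and restarts at dose 2, so Day 22 up to a late dose 2 is not covered. Section 6.4 collects continuously from dose 1, and the dose 2 visit assesses unsolicited AEs, so this too is a conflict of text and not a real hole in collection.

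**The case against.** The best defence is that Day 49 and Day 35 are nominal. Section 5.5.2 writes Day 49 as a gloss on 28 days after the second vaccination, the immunogenicity endpoints gloss Day 35 in the same way, and footnote b calls days relative to vaccination estimates. Section 7.3 leaves analysis detail to a SAP that is not at hand and may apply the right window. This probably explains the wording of section 6.4. It does not rescue section 7.3.3 or the synopsis, which count explicitly from the first vaccination.

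Several stronger readings are tempting but not supported:

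- **That the cut-offs lose half of the 28-day AE window.** The Day 35 cut-off governs all MAAEs only. For in-window dosing, Day 49 costs at most 25% of the AE window. Half is the MAAE figure for dose 2 on Day 28.
- **That everyone has 14 uncovered days and only spontaneous reports remain.** The stretch is 7 to 14 days. Section 6.4.1.2 puts a standard question about changes in well-being, hospitalisation and medication at every study visit, which includes the 3-month visit. Section 6.4.1.3 requires all reported AEs to be recorded, and section 6.4.1.1 tells participants to make contact at any time if symptoms develop.
- **That the reactogenic period after dose 2 is missed.** Section 1.3 does report greater reactogenicity after second vaccinations, but of short duration (mean of 2 days or less). The first 7 days after an in-window dose 2 lie inside every window.

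The same rules also apply to both blinded arms.

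**Conclusion.** The contradiction stands, at moderate severity. The analysis text, applied as written, shortens a secondary safety endpoint for anyone who receives dose 2 after Day 21. For in-window dosing the loss is up to 7 of 28 unsolicited-AE days (25%) and up to 7 of 14 all-MAAE days (50%). These are not upper bounds overall, because out-of-window dosing has no stated limit. The size in practice depends on the actual dose 2 dates and on whether the SAP follows section 7.3.3; neither is known from the protocol.

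The lack of a listed unsolicited-AE visit over the last 7 to 14 days makes ascertainment later and more passive. It does not remove those days from the endpoint.

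A reader might infer that the trial's main conclusions are at risk. They are not: primary efficacy, alpha and sample size do not depend on these windows, and SAEs, AESIs and related MAAEs run to end of study. The exposure is mainly to non-serious unsolicited AEs and unrelated MAAEs.

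**What to change.** In sections 6.4, 6.4.1.1.4 and 7.3.3, the synopsis, and footnotes u and v of Table 3-1, use one definition: collection and analysis run continuously from dose 1 through 28 days (unsolicited AEs) and 14 days (all MAAEs) after the actual date of dose 2. Keep Day 49 and Day 35 only as nominal days. For in-window dosing the windows then end on Days 49 to 56 and Days 35 to 42, and no promised days are dropped. The cost is protocol wording and a matching derivation in the analysis programs.

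As an optional addition, list unsolicited AEs with onset up to 28 days after dose 2 at the existing 3-month visit (Table 3-1 and section 6.1.6). This costs one schedule entry and one eCRF question. Its weakness is recall over roughly 7 to 13 weeks. The weekly text or email is not a ready substitute, because it prompts only for symptoms or concerns that could be SARS-CoV-2 infection.

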7.3.3.1 Safety: Study Vaccine-Associated Enhanced Disease

Continuous monitoring for study vaccine-associated enhanced disease will be performed through the CRO and sponsor medical monitors. These events will be monitored in real-time and after each confirmed respective case. The SMC will review this data at scheduled SMC meetings throughout the study or at an ad hoc meeting if the medical monitors would like a more immediate review of the data.

7.4 Handling of Missing Data

For calculating geometric means and GMFR, immunogenicity values reported as below the LLOQ will be replaced by $0.5 \times$ LLOQ. Values that are greater than the upper level of quantitation (ULOQ) will be replaced by the ULOQ. Missing results will not be imputed.

7.5 Interim Analyses

Prior to the final analysis, 2 formal interim analyses of efficacy and futility will be conducted based on the accumulation of approximately 43% (66 events) and 72% (110 events) of the total anticipated target number of the primary endpoint (152 events). For these analyses, the data needed to perform the analysis of the primary efficacy endpoint will be cleaned. The interim analyses will be performed by an unblinded Biostatistics and Programming team, and the unblinded statistician will communicate the results of the analyses to the Sponsor in terms of fulfillment or nonfulfillment of the predefined success criterion (yes/no).

Based on the communication received from the unblinded statistician, the sponsor may choose to stop the study to unblind the accrued data or to continue the study while maintaining the blind to achieve a more robust safety and efficacy data package for the regulatory submission. Any early stopping for efficacy will be based on the PP-EFF population only. The unblinded statistician and programmer team will be isolated (by firewall) from study personnel. They will complete a review independent of the study team and sponsor. The interim analyses will follow standard group-sequential design using the Lan-DeMets alpha-spending function for O'Brien-Fleming boundary conditions. Table 7-2 summarizes the timing, number of endpoints, and statistical success boundaries at the planned interim analyses and the final analysis.

Г

Table 7-2:Interim and Final Boundaries Using O'Brien-Fleming Spending Function				
Planned Information Fraction (% of total endpoints)	Planned Blinded Total Number of Endpoints	Planned One-Sided Nominal Alpha	VE Boundary for LBCI > 30%	
Interim analysis at 43%	66	0.00063	~75%	
Interim analysis at 72%	110	0.00804	~59%	
Final analysis at 100%	152	0.02246	~51%	

Abbreviations: LBCI = lower bound confidence interval; VE = vaccine efficacy.

If an unplanned additional interim analyses is be added or the timing for an planned analysis is modified, the Lan-DeMets alpha-spending function will be used to adjust the nominal alphas to maintain the pre-specified overall one-sided type I error at 0.025.

